During self-administered nitrous oxide (SANO) a patient holds a gas mask to their own face, and works with the medical team to titrate the nitrous level to optimum concentration level. SANO is administered as a single agent of nitrous oxide, at concentrations <50%. At these levels, nitrous oxide is classified by the American Society of Anesthesiologists (ASA) as "mild sedation", which does not require the presence of anesthesia personnel, NPO status, nor escort home. Current literature states that "patients could safely operate a motor vehicle after N₂O/O₂ sedation" (Clark et al., 2020). An additional study performed by Hawkins, et al. similarly concludes that there does not appear to be any residual cortical effects from mild sedation with nitrous oxide. The recovery period was established to be three to five minutes following termination of nitrous oxide, and the expectation that participants would "return to normal at the first post-treatment determination (five minutes post-operative)" was confirmed. In each study, participants were given a 50-50 mixture of N₂O/O₂, and concentrations of NO₂ between 35-50% (Clark et al., 2020). This closely mirrors our protocol's administration of nitrous oxide, as we are administering concentrations of 25-45%.

The Nitrouseal® system has an adjustable-concentration digital flowmeter and includes an FDA-cleared exhaled waste gas scavenger, the Miniscav®. The Nitrouseal® system includes a proprietary disposable single-use full-face mask and breathing circuit that collects and contains the exhaled nitrous gas before it is scavenged into the Miniscav®.

The Nitrouseal® has been used in urology since 2017 in procedures such as vasectomies, cystoscopies, UroLift® implants, bladder biopsies, prostate biopsies and Botox injections, with reported improvement in patient anxiety, relaxation and comfort. However, there have been no controlled studies in the US that have studied the effects of nitrous oxide for UDS.

B3. DESCRIPTION OF RESEARCH PROTOCOL**A. Study Design – Overview, Methods, Procedures****METHODS AND PROCEDURES:****Screening**

After the Urologist has discussed and planned for office urodynamic study, a baseline examination by the clinical team for eligibility verification will be performed through a medical record review by a trained member of the research staff.

Recruitment and Obtainment of Informed Consent

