Confirmation of a patient's eligibility and completed informed consent will be documented in REDCap before proceeding with study procedures. Then, patients will complete the Brief Pain Inventory (see attached) via REDCap questionnaire that is sent to the patient's email. The BPI is a well-validated measure that assesses intensity of current pain and interference of pain in the patient's life (Dworkin, 2005). If the patient does not complete the BPI electronically before the day of procedure, they will be offered the opportunity to complete it on the day of their procedure prior to the UDS.

Randomization

A UDS is comprised of two phases: a filling phase and a voiding phase. For the purposes of our study, subjects will undergo two “runs”, one with SANO and one with Oxygen.

Subjects will be randomized to either:

- Group 1: First run with SANO, second run with Oxygen
- Group 2: First run with Oxygen, second run with SANO

The results of the randomization will not be disclosed to patients as part of the study (patient-blinded), or to the operator of the UDS (provider-blinded). The randomization module in REDCap will be used to randomize subjects between the two groups.

The catheters will be placed before the first run, and left in place through the second run (that is, the catheters will not be changed between the two runs). All subjects will receive SANO during catheter placement. The UDS will be performed by a BIDMC advanced care practitioner according to usual clinical practice. It is standard-of-care for patients to undergo two complete UDS runs:

- First run: Filling phase, voiding phase (~8 minutes)
- Second run: Filling phase, voiding phase (~8 minutes)

Therefore, we do not believe the utilization of two runs to be a significant increase in burden on the patient.

Pre-procedure Evaluation

On the day of the UDS, the patient will be brought to the exam room where pre-procedure vitals are obtained. The six-item State Trait Anxiety Inventory and the six-item Pain Catastrophizing Scale will be administered to assess patient’s baseline pain and anxiety levels. Information of inhaled gas administration and how to self-administer will be explained to the patient using templated verbal instructions. It will be emphasized that if at any point during the procedure, the patient feels uncomfortable with the inhaled gas, the team will help remove the mask.

Periprocedural Intervention

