The patient will be moved into the standard procedural positioning in the UDS chair. Explanation of the UDS procedure will be done in the routine manner preferred by the study technician (a Urology APP). An oxygen saturation monitor will be applied to the patient's finger and monitored throughout the procedure. The patient’s heart rate will also be monitored.

During the procedure, the patient and their oxygen saturation levels will be monitored by a [name], APP, or MD (separate from APP performing the procedure).

[figure not shown]
The inhalation gas mask will be positioned on the patient's face, and the patient will then be instructed to begin breathing as previously instructed. Initially, the patient will receive 100% oxygen at 10 liters/minute.

After the APP describes the procedure, all patients will have nitrous oxide turned on to 30%, ensuring that the patient is relaxed but still conversant through the procedure. The nitrous will be adjusted up or down based on the patient’s response to the question “are you feeling the nitrous” and “are you happy at this level”. The range will be between 25 - 45%, and will be recorded. This may take 2-3 minutes. The technician will then insert the urethral pressure catheter as well as the

abdominal catheter. We will then wash out with 100% oxygen for 2 minutes. We will perform the UDS study in the routine fashion, asking the patient to perform routine parameters such as cough, report of bladder fullness, and volitionally void. After the first run, we will again wash out with 100% oxygen for 2 minutes while we switch from SANO to oxygen (or vice versa depending on the randomization group).

At a single time-point during both runs, the operator handling SANO will ask the patient to complete a VAS-A and VAS-P. A laminated sheet will be held in front of the patient, and they will point to a number between 1 – 10 to signify their current level of anxiety (VAS-A) and pain (VAS-P). The number will be verbally confirmed by the operator handling SANO.

If at any point the patient is unhappy with gas inhalation, the observer will aid the patient in removing the mask. At the end of the procedure, the SANO group will be turned down to 0% nitrous oxide, and 100% oxygen will be administered through the mask for an additional 2-3 minutes as the patient is cleaned and post vitals obtained. Assessment of the “time in” and “time out” of the procedure room will be recorded.

Flowchart 1. Intraprocedural Study Activities

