Approximately 5-10% of patients who undergo UDS at BIDMC exhibit dizziness or vasovagal response during the procedure. This risk is solely attributed to the nature of UDS. Due to the rapid offset of SANO (2-3 minutes), we do not believe this risk to be compounded after receipt of SANO. According to standard clinical practice, the APP performing the UDS and the SANO administrator will take special care to ensure a patient is stable and able to ambulate safely after catheter removal and completion of the UDS.

Finally, as with any inhaled gas, there can be a concern of hypoxia or apnea with administration of nitrous oxide. This event has not been routinely reported in the literature as a risk or side effect of nitrous oxide. During the procedure, patients will undergo continuous oxygen saturation and heart rate monitoring. These values will be documented in REDCap as part of the patient's study records.

If there are concerns of hypoxia, either objectively by the oxygen monitoring or subjectively by the patient, the protocol will be to immediately turn off the nitrous oxide and administer 100% oxygen until vitals return to baseline. All personnel in the room will have BLS training. The Clinical Research Center has a code cart which is readily available. e proximate to areas

Possible Unauthorized Use of Nitrous Oxide

Inhalation of nitrous oxide is used/abused in recreational settings with the purpose of causing euphoria and hallucinations. To prevent potential misuse, the nitrous oxide will be stored within the operating room storage area reserved for anesthetic gases during non-office hours.

Potential for Loss of Confidentiality

There is a potential for loss of confidentiality for participants in the study. Protections will be implemented to mitigate this risk. As detailed in our protocol, we will use REDCap to collect patient information and questionnaires. Though REDCap is generally considered secure for the purposes of PHI, it is a web-based application and the data is accessible to study team members on their own personal computers. Access to our REDCap will be limited to study team members who are trained in protecting PHI. Any electronic study files or information that is not stored on REDCap will be kept on a secure directory on the BIDMC server that is only accessible to research staff.

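### Both washouts last 2 minutes, the bottom of the protocol's own 2–3 minute nitrous offset, so an Oxygen run may overlap residual nitrous by up to 1 minute

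*Protocol*

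**What the plan says.** Protocol B3.A, Periprocedural Intervention, places the catheters under SANO in all patients and then specifies: "We will then wash out with 100% oxygen for 2 minutes". Between runs it specifies: "After the first run, we will again wash out with 100% oxygen for 2 minutes while we switch from SANO to oxygen", or the reverse switch, depending on the group. When the procedure ends, "100% oxygen will be administered through the mask for an additional 2-3 minutes".

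Protocol B3.A, Randomization, sets the order. Group 1 has SANO then Oxygen, and Group 2 has Oxygen then SANO. Each run takes about 8 minutes. On the catheters it says: "The catheters will be placed before the first run, and left in place through the second run".

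The protocol describes how quickly nitrous wears off in two places:

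- B5, on the risk of dizziness in this trial: "Due to the rapid offset of SANO (2-3 minutes".
- B2, Administration, on published work about residual cortical effects and fitness to drive: "The recovery period was established to be three to five minutes following termination of nitrous oxide". Participants there were expected to "return to normal at the first post-treatment determination (five minutes post-operative", and this is reported as confirmed. Those studies used 35–50% nitrous, including a 50:50 mixture. For this trial B2 says "we are administering concentrations of 25-45" percent.

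The readable text sets no further wait before a run, and no check that the nitrous effect has ended before one begins.

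**The concern.** The Oxygen run is the comparator, and the design needs it to reflect bladder function and patient behaviour without nitrous. No Oxygen run comes without prior nitrous. In Group 2 it follows catheter placement under SANO, and in Group 1 it follows the SANO run. In each case one 2-minute washout stands between. A washout equal to the shortest stated offset leaves no margin for a patient whose offset is nearer the longer one.

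The direction matters more than the length. Aim 1 sets out to show that SANO does not alter the urodynamic results. Nitrous left over at the start of an Oxygen run would pull the two runs together, so any bias favours the result the trial hopes for.

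The measures most open to this are those that cover the whole run, opening minutes included:

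- **Operator-rated patient responsiveness.** It is collected for each run (Protocol B3.A, Periprocedural Data Collection), analysed in the SAP (Statistical Analysis), and relevant to Hypothesis 1.3.
- **Number of detrusor contractions.** It is a listed outcome in Protocol B3.B, Data Analysis.

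**Working it through.** The plan does not derive the 2-minute figure, so there is no calculation to reproduce. The check sets the washout against the protocol's own offset times.

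**Inputs**

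- Washout W = 2 min, both times (Protocol B3.A, Periprocedural Intervention)
- Trial-specific SANO offset T = 2 to 3 min (Protocol B5)
- Recovery in the cited studies T = 3 to 5 min (Protocol B2, Administration)
- Run length about 8 min (Protocol B3.A, Randomization)

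**Formula.** Overlap = max(0, T − W), as a share of the run = overlap / 8. This assumes that filling starts the moment the washout ends.

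**Current plan, W = 2**

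| Source of T | Lower end | Upper end | Share of run |
|---|---|---|---|
| B5, 2–3 min | 2 − 2 = 0 min | 3 − 2 = 1 min | 0 to 1/8 = 12.5% |
| B2, 3–5 min (upper bound only) | 3 − 2 = 1 min | 5 − 2 = 3 min | 1/8 = 12.5% to 3/8 = 37.5% |

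The first row carries the point, because it is the figure the protocol states for SANO in this trial. The reasons for holding the second row to an upper bound are given with the objections.

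**Which outcomes the window can reach.** The overlap falls at the start of the run. Maximum cystometric capacity is reached when filling ends, and the SAP (Outcomes) times the pain and anxiety scores just ahead of that point. On the B5 figure, these would fall inside the window only if filling took less than 1 minute of a run of about 8. Maximum flow and post-void residual come later still, with voiding. The documents do not say at what point of the run maximum detrusor pressure is taken, so it cannot be placed on either side.

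**With W = 3.** Against B5, max(0, 2 − 3) = 0 and 3 − 3 = 0, so there is no overlap. Against B2, 3 − 3 = 0 to 5 − 3 = 2 min.

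**Catheter time from the start of the first washout to the end of the second run**

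- Now: 2 + 8 + 2 + 8 = 20 min
- 3-minute washouts: 3 + 8 + 3 + 8 = 22 min (+2 min; 2/20 = +10%)
- 5-minute washouts: 5 + 8 + 5 + 8 = 26 min (+6 min; 6/20 = +30%)

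**The case against.** The strongest reply is that 2 minutes lies within the B5 range, so for some patients there is no overlap at all. Oxygen also continues during the Oxygen run, so nitrous keeps clearing, and an offset range does not say how much effect is left at minute 2. Nitrous is titrated so that the patient can still converse at full dose. A fading remnant in the first minute may well not shift a three-level rating of the whole run. The contraction count belongs to no stated hypothesis and is not named in the SAP text. Timing is also partly unreadable, because the intraprocedural flowchart is not shown. All of this stands, and it keeps the point small. It does not supply the missing margin.

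A reader might infer from B2 that the overlap is up to 3 minutes and that 5-minute washouts are needed. The documents do not support that. The B2 figure concerns cortical recovery at 35–50% nitrous, against 25–45% here. Five minutes was the first check, so effects may have ended sooner. B2 does say that the cited regimen closely resembles this one, so the figure is relevant, but only as a ceiling. Five-minute washouts would add 6 minutes with catheters in place, in a study of pain, anxiety and procedure time.

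A reader might also infer that the SAP offers its first-run-only sensitivity analysis as a nitrous-free comparison. It makes no such claim. It is true only that this analysis does not remove the exposure, since Group 2's first run also follows nitrous. Nor is SANO at catheter placement an error in itself, since it is common to both sequences.

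**Conclusion.** The point holds as a minor design weakness. The washout equals the shortest offset the protocol gives for SANO and falls short of the longest by 1 minute. The possible overlap at the start of an Oxygen run is 0 to 1 minute, at most 12.5% of the run, and it applies in both groups. Any bias would run towards Aim 1.

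This rests on two assumptions: that filling begins directly after the washout, and that the B5 range describes these patients. The effect on any outcome cannot be derived from the documents. A reader might infer that the primary result on cystometric capacity is compromised. The timing argues against that: capacity, the pain and anxiety scores, maximum flow and post-void residual are all read late in the run and are probably unaffected.

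**What to change.** In Protocol B3.A, Periprocedural Intervention, set both washouts to 3 minutes of 100% oxygen, the same in both groups, for any further enrolment or a follow-on trial. This covers the whole B5 range.

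The cost is about 2 more minutes per patient with catheters in place. It is equal in both groups, so it does not favour either sequence. No extra patients and no new data items are needed.

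For the 19 participants already analysed, nothing needs to be re-run. State the 2-minute washout beside the responsiveness and detrusor contraction results.

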#### Please note:

In our original study protocol, we had based our sample size calculation on a study by Jeon et al. However, as the inter-class correlation was not reported in the study by Joen et al., using their study increases our risk of a type 2 error. In light of this, we performed a literature review of all studies comparing cystometric capacity on repeat cystometry to identify a study that also reports inter-subject correlation. Using the maximum cystometric capacity (MCC) by Broekhuis et al., with an interclass correlation coefficient of 0.86, the sample size calculation to detect clinically relevant a priori difference in 50mL with a power of 82% was 16 patients total. The resulting sample size is less than the amount recruited in our study (19), thus the risk of a type 2 error is less than 20%. The below statistical analysis reflects our updated design.

### *Outcomes*

An intention-to-treat analysis was performed on 19 participants. MCC was measured as the primary outcome. Secondary outcomes included patient-reported pain and anxiety measured at baseline and immediately before maximum capacity during each UDS run using the Visual Analog Scale for Pain (VAS-P; range 0-10) and the Visual Analog Scale for Anxiety (VAS-A; range 0-10).

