Nitrous oxide is an inhaled analgesic that is used in pediatric and adult populations for ambulatory procedures, and is largely viewed as effective and safe. Nitrous oxide also produces a dissociative euphoria and amnesia that could potentially improve patients' anxiety and experience of care during painful or anxiety provoking procedures. We have used patient self-administered nitrous oxide (SANO) in our ambulatory clinic at BIDMC for men undergoing prostate biopsies with good effect and no significant complications. SANO may offer an appealing option for patients who are reluctant to undergo an initial UDS or for those who have not tolerated the study in the past. What we do not know is whether a UDS performed under the influence of SANO will give study results that are accurate and reproduce the bladder function of the patient during their daily routine. In a pediatric population, both ketamine and midazolam have been shown to provide satisfactory sedation without impacting UDS values (Thevaraja, 2012); however, sedation with propofol does negatively impact outcome values (Merguerian, 2006). No studies to date assess whether the administration of SANO will negatively impact UDS results. It is possible that SANO will perform better than ketamine or midazolam, as it is anticipated SANO will reduce anxiety and perception of pain without causing a sedative effect.

We propose a pilot study with 25 patients (14 randomized) to compare the impact of SANO vs Oxygen on UDS parameters of patients undergoing routine UDS. Study procedures will take place in the Clinical Research Center (ST 802, Gryzmish 8). Our primary aim will be to assess whether SANO has any adverse effects on routinely measured UDS variables. We will assess whether

periprocedural SANO negatively impacts operator productivity or increases the difficulty in performing the UDS. A secondary aim will be to assess patient perceived pain and anxiety related to catheter placement and experience of SANO during the UDS.

Specific Aims:

Aim 1: To demonstrate that Self-Administered Nitrous Oxide (SANO) at the time of Urodynamic Study (UDS) does not significantly impact outcome variables during the study.

Hypothesis 1.1: Administration of periprocedural SANO will not impact core UDS outcomes of “Bladder Capacity”, “Maximum Flow Rate”, and “Maximum Detrusor Pressure”

Hypothesis 1.2: Administration of periprocedural SANO will not significantly lengthen the time of the procedure

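### Aim 1 seeks to show that nitrous has no effect, yet no stated analysis takes account of gas actually received, so any interrupted SANO run would favour that conclusion

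*SAP*

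**What the plan says.** The Protocol (B1, Specific Aims) sets Aim 1 as showing that SANO "does not significantly impact outcome variables during the study", with bladder capacity, maximum flow rate and maximum detrusor pressure as the core outcomes. The SAP makes MCC primary. It compares the SANO and Oxygen runs with a paired Wilcoxon test at alpha 0.05 and a Hodges-Lehmann estimate with 95% CI (SAP, Statistical Analysis). It states no equivalence margin.

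On the analysis set, the SAP (Outcomes) says: "An intention-to-treat analysis was performed on 19 participants". Nineteen is also the number it reports as recruited. It adds a subgroup analysis by randomised sequence and a sensitivity analysis of the first run only.

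On exposure, the Protocol gives two routes by which a SANO run can lose its nitrous:

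- B3, Periprocedural Intervention: "If at any point the patient is unhappy with gas inhalation, the observer will aid the patient in removing the mask".
- B5, risks of nitrous oxide, on concern about hypoxia: "the protocol will be to immediately turn off the nitrous oxide and administer 100% oxygen until vitals return to baseline".

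The Protocol says the nitrous level, within a range of 25 to 45%, is recorded. It says so while describing titration before catheter placement. It does not tie the record to each run, and no stated analysis uses it.

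**The concern.** In a trial that seeks a difference, intention-to-treat is the cautious choice, because poor exposure works against the sponsor's hypothesis. Here the direction is reversed. The hoped-for result is no difference, judged by a test of difference without a margin, so anything that makes the two runs alike helps the conclusion.

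A SANO run with no nitrous on board when MCC is read is in effect a second Oxygen run, and its expected contribution to the paired difference is near zero. A mask removed during an Oxygen run does not have this effect, since that run is nitrous-free either way.

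Without exposure information, a reader cannot tell whether a small difference means that nitrous has little effect or that some SANO runs had little nitrous. That matters because the stated purpose is to decide whether urodynamic results obtained under SANO can be trusted.

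**Working it through.** **Inputs from the SAP (note on sample size; Statistical Analysis).** "the sample size calculation to detect clinically relevant a priori difference in 50mL with a power of 82% was 16 patients total", "with an interclass correlation coefficient of 0.86", alpha 0.05 (two-sided assumed) and 19 recruited and analysed. The SD of MCC is not given. Nor is k, the number of SANO runs without nitrous at capacity, so k is an assumption throughout.

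**Step 1. The plan's own figure.** Sixteen patients cannot be reproduced independently without the SD. Working backwards with a two-sided paired t test, 16 patients, 82% power and 50 mL imply an SD of the difference of 65.0 mL. With correlation 0.86, the SD of MCC is 65.0 / √(2 × (1 − 0.86)) = 65.0 / √0.28 ≈ 123 mL. At n = 19 the same SD gives 88.7% power. On that footing, the SAP's statement of a type 2 error below 20% is consistent with its inputs.

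**Step 2. Dilution of the effect.** Let k of 19 SANO runs have a true effect of zero and the rest a true effect of 50 mL. The expected mean difference is 50 × (19 − k)/19, so each such run removes 50/19 = 2.6 mL. This step needs no SD.

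**Step 3. Effect on power, for illustration.** The SD of the difference is taken as 65.0 mL and n = 19. Power is simulated with the planned Wilcoxon test (4,000 replicates) and with a paired t test (200,000 replicates).

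| k | Expected mean difference (mL) | Wilcoxon power | Paired t power |
|---|---|---|---|
| 0 | 50.0 | 87% | 89% |
| 1 | 47.4 | 83% | 85% |
| 2 | 44.7 | 78% | 79% |
| 3 | 42.1 | 72% | 74% |
| 4 | 39.5 | 65% | 67% |

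Under this assumed SD, one affected run leaves power above the stated 82%. Two bring it just under 80%.

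**Step 4. Dependence on the SD.** With no affected runs at all, paired t power at n = 19 is 97%, 90%, 85%, 74% and 58% for an SD of MCC of 100, 120, 130, 150 and 180 mL. The power column is therefore only as good as the back-solved SD. The column in mL is not affected.

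**Step 5. Do the other stated analyses help?** The subgroup analysis splits patients by randomised order. The sensitivity analysis compares first runs between the randomised groups. Neither is restricted by gas received, so an interrupted SANO run would count as SANO in both.

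**The case against.** The strongest reply is that nothing shows any run was affected. The Protocol describes hypoxia as not routinely reported with nitrous, gives a vomiting risk below 0.5% for this system, and reports previous use in the clinic without significant complications. With k = 1 the loss is 2.6 mL of 50. A staff member other than the operator monitors the patient, and the person handling the gas takes the VAS scores, which the SAP places just before capacity, so someone is well placed to notice a lapse. An exposure-based set also selects on an event after randomisation. All of this stands. It limits the size of the concern and fixes the role of the extra analysis as a supplement. It does not supply the missing count.

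A reader might infer more than the documents support:

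- **That intention-to-treat is the only analysis.** It is the only analysis set named in the available text; two further analyses are stated, though neither addresses exposure.
- **That SANO runs begin without nitrous.** The Protocol says, after catheter placement, "We will then wash out with 100% oxygen for 2 minutes", and then moves to the study without describing how nitrous is re-established for a first SANO run. However, it does mention a switch of gas between runs, and the flowchart is not shown. With titration of 2 to 3 minutes in a run of about 8 minutes, this would suggest low exposure early in filling. MCC is reached at the end of filling, so it does not show that nitrous was absent there.
- **That patients who react most to nitrous remove the mask most.** The Protocol's trigger is dissatisfaction with the gas. No link to any bladder effect is documented.
- **That interrupted runs were in fact counted as SANO.** This follows from the intention-to-treat label and silence on handling; no explicit rule says so.

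**Conclusion.** The concern holds as a gap in the analysis plan. It does not demonstrate bias in the result. For a claim of no impact, intention-to-treat alone is the less cautious set, the Protocol allows SANO runs to lose their nitrous, and no stated analysis checks whether that mattered.

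The direction of any bias is towards no impact, provided that an interrupted run is completed and analysed as SANO. Its size is unknown, because k is unknown and may be zero. A true 50 mL effect would appear as 47 mL for k = 1, 45 mL for k = 2 and 39 mL for k = 4, taking affected runs as wholly unexposed at MCC; partial exposure would dilute less. The SAP reasons that, with 19 patients against the 16 it needed, its type 2 error lies below 20%. With the back-solved SD of the difference of 65.0 mL, two affected runs would be enough to undo that statement. With another SD the threshold would move.

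**What to change.** 1. From the existing records, report how many SANO runs had the mask removed, the nitrous turned off, or a recorded level outside the Protocol's own 25 to 45% range. If the records do not show this for each run, say so.
2. Add a paired sensitivity analysis of MCC, Qmax and Pdet max that excludes patients with such a SANO run. Use the same Hodges-Lehmann estimate and 95% CI, and present it beside the intention-to-treat result.
3. Qualify the no-impact conclusion if the two estimates or intervals differ materially. For MCC, the SAP's own 50 mL is a natural yardstick: for example, if one interval reaches 50 mL and the other does not. If the count is zero, report that; the conclusion is then stronger.
4. Reconcile the Protocol's text on washout and on establishing nitrous before a SANO run with the flowchart.

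The cost is one count and one further analysis. The downside is a smaller set, a wider interval and selection after randomisation, so this analysis supplements intention-to-treat and does not replace it. The SAP reports the runs as already done, so flowmeter readings tied to MCC can be added only in a future study. No change to the rules for removing the mask or stopping the gas is implied.
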